### 6.5.5 12-Lead ECG, QTc

No analyses of ECG will be performed.

### 6.5.6 Other safety measures

For each treatment group, vital signs (i.e. blood pressure, heart rate, weight and BMI) will be tabulated and summarized by visit for observed values and changes from baseline using descriptive statistics, as appropriate. If more than one baseline assessment was collected, the most recent one will be used. If several assessments are performed on the same day (without timing information) the average of the values will be considered.

Outlier analyses will be conducted using the following limits:

- low systolic blood pressure:  $\leq 90$  mmHg and a decrease of  $\geq 20$  mmHg
- high systolic blood pressure:  $>190$  mmHg and an increase of  $\geq 20$  mmHg
- low diastolic blood pressure:  $\leq 50$  mmHg and a decrease of  $\geq 20$  mmHg
- high diastolic blood pressure:  $> 105$  mmHg and an increase of  $\geq 20$  mmHg

- low heart rate: < 50 bpm and a decrease of  $\geq 15$  bpm
- high heart rate: > 120 bpm and an increase of  $\geq 15$  bpm

The number and percentage of patients with outlying values will be tabulated by treatment group and time interval.

No subgroup analyses will be performed.

Unscheduled vital signs data will be included in the summary tables.

### **6.5.7 Physical examinations**

The number and percent of patients with physical examination abnormalities will be summarized based on the safety analysis set for each treatment group and overall. Physical examination findings will be presented in a data listing.

No subgroup analyses will be performed.

## **7. Document history and changes in the planned statistical analysis:**

SAP Version 4.2 dated 20 SEP 2018

Supplemental 4 SAP version 1.0 dated 04DEC2019

Supplemental 5 SAP version 1.0 dated 27JAN2020.

## **8. References**

Refer to main SAP v4.2 dated 20 SEP 2018.

## List of Abbreviations

AE	Adverse Event
ADT	Androgen Deprivation Therapy
ANCOVA	Analysis of covariance
AUC	Area under the curve
BMI	Body Mass Index
BPI-SF	Brief Pain Inventory – Short form
CYTOC	Cytotoxic Chemotherapy
CI	Confidence Interval
CRF	Case Report Form
DMC	Data Monitoring Committee
EBRT	External beam radiation therapy
ECG	Electrocardiogram
ECOG	Eastern Cooperative Oncology Group
EORTC-QLQ-PR25	European Organization for Research and Treatment of Cancer quality of Life Questionnaire- Prostate Cancer Module
EQ-5D-3L	European Quality of Life 5 – Domain scale
EWB	Emotional well being
FACT-P	Functional assessment of cancer therapy Prostate
FAS	Full Analysis Set
FWB	Functional well being
HRQoL	Health Related Quality of Life
HLT	High level term
IRT	Interactive response technology
ITT	Intent-to-treat
IPE	Iterative Parametric Estimation
IVRS	Interactive voice response system
MedDRA	Medical Dictionary for Regulatory Activities
MFS	Metastasis-Free Survival
MLG	MedDRA Labelling Grouping
n	Number of non-missing values
N/A	Not Applicable
NCI-CTCAE	National Cancer Institute Common Terminology Criteria for Adverse Events
nmCRPC	Non-metastatic castration-resistant prostate cancer
OM	Operational manual
OS	Overall Survival
PCS	Prostate cancer subscale
PCWG2	Prostate Cancer Trials Working Group2
PDD	Protocol Deviations Document
PFS	Progression-free Survival

---

PK	Pharmacokinetics
PPS	Per-Protocol Set
PRO	Patient Reported Outcome
PSA	Prostate-specific antigen
PSADT	Prostate-specific antigen doubling time
PT	Preferred Term
PWB	Physical well being
QoL	Quality of Life
QTc	Corrected QT
QTcB	Corrected QT Bazaett's formula
QTcF	Corrected QT Fredericia's formula
RECIST	Response Evaluation Criteria in Solid Tumors
RPSFT	Rank-Preserving Structural Failure Time
SAE	Serious Adverse Event
SAC	Statistical Analysis Center
SAF	Safety Analysis Set
SAP	Statistical Analysis Plan
SDG	Standardized Drug Grouping
SSE	Symptomatic skeletal event
SOC	System organ class
SWB	Social family well being
TEAE	Treatment-Emergent AE
TOI	Trial Outcome Index
US	United States
WHO-DD	World Health Organization Drug Dictionary

## 1. Introduction

Study 17712 (ARAMIS) is a multinational, randomized, double-blind, placebo-controlled, phase III efficacy and safety study of darolutamide in men with high-risk non-metastatic castration-resistant prostate cancer (nmCRPC).

This statistical analysis plan (SAP) describes the analyses and data presentations for final primary efficacy endpoint (metastasis-free survival) and the final overall survival analysis at the end of double-blind part when targeted number of primary endpoint events is collected.

The SAP contains definitions of analysis sets, derived variables, and statistical methods for the analysis of efficacy and safety.

This SAP version 4.2 is an updated of SAP version 4.1 dated 13SEP2018 which was an update of version 4.0 dated 10AUG2018 and version 3.0 dated 12MAR2018. SAP v3.0 is based on the integrated protocol version 4.0 (amendment 3), dated 26 FEB 2018, is an amendment of the abbreviated SAP version 2.1 dated 22 JUN2017, based on protocol version 3.0 (amendment2), dated 19 JUL 2016.

## 2. Study Objectives

The primary objective of the study is to demonstrate superiority of darolutamide over placebo in metastasis-free survival (MFS) in patients with high-risk non-metastatic castration-resistant prostate cancer (nmCRPC).

The secondary objectives of the study are:

- Overall survival (OS),
- Time to pain progression,
- Time to first symptomatic skeletal event (SSE),
- Time to initiation of first cytotoxic chemotherapy for prostate cancer,
- Characterize the safety and tolerability of darolutamide.

The additional objectives of the study are:

- Progression free survival (PFS),
- Time to first prostate cancer related invasive procedure,
- Time to initiation of first subsequent antineoplastic therapy,
- determine effect of darolutamide on prostate-specific antigen (PSA) progression and PSA response
- ECOG performance status deterioration

- Health-related quality of life (QoL)
- Evaluate pharmacokinetics (PK) of darolutamide and keto-darolutamide
- Explore possible relationships between exposure and safety and efficacy response.

### 3. Study Design

This is a randomized, phase III, multi-center, double-blind, placebo-controlled efficacy and safety study of oral darolutamide (600 mg twice a day [bid]) in patients with nmCRPC who are at high risk for developing metastatic disease.

Approximately 1500 patients will be randomized to receive darolutamide or placebo in a 2:1 ratio in a double-blind manner. Randomization will be stratified by prostate-specific antigen doubling time (PSADT) ( $\leq 6$  vs.  $> 6$  months) and use of osteoclast-targeted therapy (yes vs. no). Randomized patients will receive study treatment until confirmed metastasis or intolerable adverse event (AE).

The study has a design of 2 parallel groups. For each patient, the study may involve 1 to 2 variable length periods: a study treatment period (a double-blind part for darolutamide or placebo arms and an open-label darolutamide treatment phase) and a follow-up period.

The length of the periods for each patient will depend on the absence or presence of metastasis – after confirmed metastasis, the patient must be withdrawn from study treatment.

During the double-blind part, patients may be on study treatment (darolutamide or placebo arm) or at follow-up. After the double-blind part, patients may be on open-label study treatment if they are in the darolutamide arm or if they have received double-blind placebo treatment and have started open-label darolutamide treatment in case of positive study results. Once the study results are available, and if they support a positive benefit/risk assessment for darolutamide in the study by the judgment of the sponsor, also considering feedback from the study steering committee and/or health authorities, those patients who are on study treatment (darolutamide or placebo) will be offered the opportunity to receive darolutamide through open-label treatment in this study.

The double-blind treatment (darolutamide or placebo arm) is planned to be continued until the total number of events for the primary efficacy analysis (MFS analysis) had been reached (approximately 385 events). During this part the treatment code will remain blinded.

#### **Randomization and blinding:**

Randomization will be performed centrally blocking by center according to the design of the study using a 2-step procedure. Firstly, a separate master randomization schedule and study treatment package list will be created using randomly permuted blocks. Secondly, randomly permuted blocks from the master randomization schedule are assigned to the study centers. An interactive response technology (IRT) (also called interactive voice response system [IVRS]) system assigns patients to receive either darolutamide or matching placebo using allocation ratio 2:1, respectively.

The numbers are assigned to the unique patient number previously allocated by the investigator. The randomization will be stratified by:

- PSADT ( $\leq 6$  months vs.  $> 6$  months),
- Osteoclast-targeted therapy at randomization (yes vs. no).

Details of the randomization method will be given in the IRT user requirements.

The reference for this study will be placebo tablets that match the darolutamide tablets. During the double-blind part of the study at the time of radiographic metastasis patient's treatment assignment will remain blinded.

All patients, study personnel, and sponsor's personnel directly involved in the conduct of the study will be blinded to treatment assignments during the double-blind part of the study. After completing the double-blind part the study will be unblinded for the primary analyses.

### **Schedule of procedures:**

Efficacy and safety measurements obtained during the course of the study are summarized in the schedule of assessments, see Appendix 9.1.

### **3.1 Determination of Sample Size**

Several clinical publications were used as basis for the sample size calculation. The median MFS for placebo is based on denosumab phase III study results [8] at the time the ARAMIS protocol was designed, no data were available on the expected treatment effect size for androgen-receptor inhibitors in high-risk nmCRPC patients. Data published in 2016 and recently published data from SPARTAN and PROSPER phase III trials indicate, that the treatment effect of the class of novel androgen receptor inhibitors (enzalutamide, apalutamide) is stronger than initially assumed

Given the results from PROSPER and SPARTAN, the initial assumption for the treatment effect size of a hazard ratio of 0.75 was considered as too conservative.

All patients had to have an independent evaluation of radiological images for no baseline metastases at baseline to be eligible for randomization. However, for the central efficacy review, the baseline scans were again reviewed. During this review some patients were identified with metastases at baseline; to calculate sample size these patients are considered as having a MFS event on the date of randomization.

The number of events has been adjusted to account for the non-informative character of baseline metastases events and the dilution impact to the estimated MFS hazard ratio.

The assumptions used in determining the sample size for this study are as follows:

- Overall 2-sided type I error rate: 0.05,
- Assumed hazard ratio of 0.65,

- Accounting for 5% of the patients with baseline metastasis, diluted hazard ratio of 0.71,
- Randomization ratio: 2:1
- Statistical power at the final analysis: 91%,
- Median MFS for placebo: 25 months,

385 MFS events will provide approximately 91% power to detect a statistically significant difference in MFS times, with a two-sided log-rank test with a 0.05 level of significance. With 40 months accrual time and a dropout rate of 40%, the study will require approximately 1500 patients (1000 darolutamide patients, 500 placebo patients) to achieve the targeted 385 MFS events. The MFS analysis will be performed when the targeted number of approximately 385 MFS events has been observed.

This sample size calculation was performed with a simulation based algorithm.

## 4. General Statistical Considerations

### 4.1 General Principles

The statistical evaluation will be performed by using the software package SAS release 9.2 or higher (SAS Institute Inc., Cary, NC, USA).

All variables will be analyzed by descriptive statistical methods.

In general, continuous variables will be summarized using number of non-missing values (n), number of missing values, means, standard deviations, medians, maximum, minimum, and interquartile range.

Ordinal variables will be summarized using n, number of missing values, medians, maximum, minimum, and interquartile range.

Categorical variables will be summarized using n, number of missing values, and percentages.

Time-to-event variables will be summarized using Kaplan-Meier estimates.

Frequency tables will be generated for categorical data.

### 4.2 Handling of Dropouts

Patients withdrawn from study treatment will not be replaced. Refer to section 4.7 in the study protocol for withdrawal of patients from study.

All primary efficacy analyses are based on the Full Analysis Set (FAS) that comprises all randomized patients, including patients who withdraw regardless of the reason for withdrawal. The intent-to-treat (ITT) population set mentioned in the protocol is identical to

the FAS. See following chapters for more details on deriving efficacy endpoints in case of missing data.

### 4.3 Handling of Missing Data

All missing or partial data will be presented in the patient data listing as they are recorded on the Case Report Form (CRF).

When appropriate, the following rules will be implemented so as not to exclude patients from statistical analyses due to missing or incomplete data.

Missing or unevaluable tumor assessments “including scheduled assessments that were not done and incomplete assessments that did not result in an unambiguous occurrence of first metastasis or evaluation of local regional disease progression” will not be used in the calculation of derived efficacy variables related to tumor assessments unless a new lesion occurred or the lesions that were evaluated already showed metastasis. No imputation will be performed for unevaluable or missing tumor assessment. For example, if a patient misses a scan visit and metastasis is documented at the next available scan visit, the actual visit date of the first documented metastasis will be used to calculate MFS.

If a date is incomplete, (e.g. only year and month of date of tumor assessment or date of death is available), then day 15 of the month will be used for the calculation of, for example, MFS, OS.

If the actual scan date of the radiological metastasis is missing and radiological metastasis has been documented based on criteria specified in the protocol, the scheduled scan date will be used to calculate the time to metastasis.

If date for QoL questionnaire is not documented, then the corresponding visit date will be used.

#### **Safety variables, Medical history, and Concomitant medications:**

Treatment emergent AEs, treatment phases, period and relative days will be derived according to data management programming, the operational manual document and standard guidelines.

### Missing Patient report Outcome (PRO) data

In case of missing responses for one or more items, subscale scores can be prorated (see scoring of FACT-P, EORTC-QLQ-PR25, Brief Pain Inventory – Short form (BPI-SF) and of EQ-5D-3L in Appendices 9.2 to 9.5).

For FACT-P this is done by multiplying the sum of the subscale by the number of items in the scale, then dividing the number of items actually answered. Prorating of scores is acceptable as long as more than 50% of the items are answered (assuming that the score of missing items are similar to those of non-missing items). If less than or equal to 50% of the items are answered for any domain, then the score of that domain is set to missing. The total score is then calculated as the sum of the un-weighted subscale scores. Moreover, the FACT-P total score is set to missing if the related overall item response rate is less than or equal to 80%.

For EQ-5D-3L, if there is a missing or ambiguous answer (i.e. marking of more than one answer) on the 5-dimension questions, then the index score is missing.

For BPI-SF 2 scores will be derived: 1/ for the pain severity score if one missing answer then scoring will be set to missing, 2/ for the pain interference score if 4 or more missing answers out of the seven questions then the score will be set to missing.

For EORTC-QLQ-PR25, six scales are created, if less than or equal to 50% of the items are answered for any scales, then the score of that scale is set to missing.

## 4.4 Interim Analyses and Data Monitoring

No formal interim analysis will be performed for primary endpoint MFS.

A formal interim analysis for secondary endpoints will be performed by the sponsor at the same time as the primary endpoint analysis. See more details in Section 6.2.

A Data Monitoring Committee (DMC) (also called Data and safety monitoring board (DSMB)) was instituted in order to ensure the ongoing safety of the patients. The operation of the DMC is guided by a DMC charter.

The DMC includes 3 independent disease experts (physicians) and one independent statistician. The DMC will operate independently of the Sponsor and Investigators. Data review meetings will be held periodically as per separate DMC charter. Enrollment into the study is to continue throughout the scheduled meetings of the DMC. The Statistical Analyst Center (SAC) is scheduled to receive the randomization list for their unblinding. Data which may compromise the integrity of the study (e.g., comparative data and/or any unblinded data) are to be analyzed and discussed only in the closed session of the DMC meetings. The closed session will be restricted to the DMC members and a non-voting facilitator (biostatistician from the SAC). Closed session minutes will be maintained by the DMC in confidence. All

data provided to the DMC and all deliberations of the DMC are to be considered privileged and confidential. DMC members signed confidentiality agreements.

#### 4.5 Data Rules

Generally, for each date stored in the database, a set of organizational variables will be derived in order to describe the temporal context of that date in the specific study: phase of treatment (pre, during or post study treatment), day relative to the start of study treatment, day relative to the end of study treatment.

Additional contextual variables may be created in analysis datasets.

Refer to Section 4.3 for handling of missing data, as well as to Section 6, for specific endpoints data rules, for example censoring patients or definition of treatment-emergent adverse events (TEAEs).

All derived variables will be stored in analyses data sets (ADS) created by the statistician and / or the statistical analyst.

Since differences may occur between the values of the stratification variables entered by the investigator at the time of randomization (IVRS) and those collected on the CRF, the analysis will be performed using both assignments to the strata. However, the primary stratified analyses for the efficacy endpoints will be based on the information collected in the IVRS whereas stratification information entered in the CRF (considered the 'true' information) will be used for sensitivity analyses. In rare circumstances, if CRF data cannot be documented, then IVRS data will be used.

Baseline data for stratification will be taken from the last non-missing observation on or before the randomization date.

Baseline data for demographics and characteristics, PRO questionnaires and safety will be taken from the last non-missing observation on or before the first day of study drug intake.

Reported outcome questionnaires dates of completion were not collected therefore the dates of corresponding visit will be used for analyses.

Unscheduled visits will be considered in analyses, excepted for analyses of health-related QoL.

A data cut-off date for the final and the interim efficacy analyses will be chosen.

Time to event variables values will be displayed in months. Months will be calculated dividing days by 30.44.

#### 4.6 Blinded Review, Validity Findings, and Protocol Deviations

Protocol deviations and validity review will be performed as described in the sponsor's operational instruction on conducting blind review meetings, cleaning, and reviewing study

data, in addition to detailed guidance on important deviations and validity findings. Any unscheduled assessments prior to randomization will be included in the determination of the baseline value.

#### **4.6.1 Blinded Review**

Blinded review will be conducted prior to database lock for each analysis, as described in the sponsor's operational instruction on conducting blinded review meetings. Reviewers will be tasked with evaluating the overall quality and reliability of the study data and its suitability for the planned statistical analysis. Blinded review will also assess protocol deviations and validity findings.

#### **4.6.2 Validity Findings**

Criteria for validity, i.e. eligibility for each analysis set, are described in Section 5. Details may be further described in a separate document. Validity findings will be obtained as described in both the sponsor's operational instruction on cleaning and reviewing study data, and the sponsor's detailed guidance on important deviations and validity findings, and includes major protocol deviations as described in Section 4.6.3 and the separate Protocol Deviations Document (PDD). The blinded review will review and finalize the validity findings prior to the database lock for each analysis.

#### **4.6.3 Protocol Deviations**

Protocol deviations will be classified as major or important. Major protocol deviations are deviations affecting analysis set eligibility or treatment group assignment and constitute validity findings as described in Section 4.6.2.

Major protocol deviations will be identified based on the criteria described in the sponsor's operational instruction on cleaning and viewing study data. Assessment criteria, deviation definitions, methods of evaluation, and further details will be described in a separate PDD.

### **5. Analysis Sets**

All patients who were randomized are included in the **Full Analysis Set (FAS)**. Following the intent-to-treat (ITT) principle, the patients in this set will be grouped according to the treatment they were allocated to receive at randomization, irrespective of actual treatment. The FAS is the primary analysis set for the efficacy analyses.

In contrast to wording from the protocol, a Per Protocol data Set (PPS) will not be specified and any per protocol analysis will not be performed as its additional value is minor.

All patients who were randomized and received at least one dose of study treatment will be included in the **Safety Analysis Set (SAF)**. This set of patients will be grouped for analysis according to the treatment they actually received, as opposed to the treatment they were allocated to receive at randomization. Only patients who solely received placebo treatment will be analyzed under the placebo arm. Patients who received at least one dose of

darolutamide treatment will be analyzed under the darolutamide arm. The SAF will be used for all safety analyses.

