## 1. Introduction

Study 17712 (ARAMIS) is a multinational, randomized, double-blind, placebo-controlled, phase III efficacy and safety study of darolutamide in men with high-risk non-metastatic castration-resistant prostate cancer (nmCRPC).

This supplement to the statistical analysis plan (SAP) describes the analyses and data presentations for final clinical study report addendum when all patients have discontinued the trial.

This SAP Supplemental 7 version 1.0 is based on integrated protocol version 5.0 (amendment 4) dated 06 JUL 2019, on Supplemental 4 SAP version 1.0 dated 04 DEC 2019 and SAP v4.2 dated 20 SEP 2018.

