### **5. Analysis Sets**

Refer to main SAP v4.2 dated 20 SEP 2018.

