Once the study results are available, and if they support a positive benefit/risk assessment for darolutamide in the study by judgment of the Sponsor (considering feedback from the study steering committee and/or health authorities), those patients who are on study treatment (darolutamide or placebo) will be offered the opportunity to receive darolutamide through open-label treatment in this study. This may dilute the effect size for the secondary endpoints as the placebo arm outcomes will become more similar to the darolutamide arm outcomes. The amount of this bias can be approximately assessed by established crossover adjustment methods like Rank-Preserving Structural Failure Time (RPSFT) [7] or Iterative Parametric Estimation (IPE) [5]. These methods construct a placebo arm Kaplan-Meier curve which is expected to resemble the Kaplan-Meier (KM) curve which would be observed if placebo to darolutamide crossover would not had occurred. The data of the second analysis of OS will be analyzed in addition with the RPSFT and IPE methods. Only the unadjusted OS data will be used for testing for a statistically significant treatment effect.

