## 6.5 Safety

No formal statistical tests will be done for the safety endpoints. All analyses for safety will be performed in the SAF population.

An updated analysis of safety events will be performed as of the final OS analysis.

Specific tables of adverse events will be displayed by following subgroups:

- Age (years) :<65, 65 - 74, 75 - 84, ≥85,
- Geographical region (North America, Asia Pacific, ROW).
- Renal function - eGFR at baseline (normal vs.mildly impaired vs. moderately impaired, severely impaired and end stage renal disease) (for calculation see Section 6.1.2),
- Hepatic impairment at baseline (normal vs mild vs moderate and severe impairment) (for calculation see section 6.1.2),
- Concomitant statin use (no vs. yes), to be determined by concomitant medication (see Appendix 9.9).

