### 6.5.1 Extent of exposure

Extent of exposure will be summarized for the SAF by treatment group, using descriptive statistics.

Duration of study treatment will be calculated in days and presented in months as the date of the last dose of any study treatment – date of the first dose of any study treatment + 1.

Dose modification will be summarized.

Extent of exposure will be described by age groups and geographical regions.

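### SAP v4.2's safety-set rule has no open-label exception: unless Supplement 4 or 5 overrides it, the final-OS safety update would report crossover patients' placebo-period data under darolutamide (with a minor person-time mismatch in the event rate)

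*SAP*

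**What the plan says.** **Arm assignment.** SAP v4.2, Section 5, states: "Only patients who solely received placebo treatment will be analyzed under the placebo arm". A patient with at least one darolutamide dose goes to the darolutamide arm, and this set serves every safety analysis. No limit to the double-blind period is given.

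The same SAP expects crossover. Section 3 counts the open-label phase as part of the study treatment period and describes patients for whom "they have received double-blind placebo treatment and have started open-label darolutamide treatment in case of positive study results". Section 6.2.2.1 says that "those patients who are on study treatment (darolutamide or placebo) will be offered the opportunity to receive darolutamide through open-label treatment". Section 6 plans summaries for two treatment groups. Section 6.5 adds: "An updated analysis of safety events will be performed as of the final OS analysis". Section 6.5.1 measures exposure across both phases: "Duration of study treatment will be calculated in days and presented in months as the date of the last dose of any study treatment", minus the date of first dose, plus 1.

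**Supplement 7** covers the final study report addendum. It is based in part "on Supplemental 4 SAP version 1.0 dated 04 DEC 2019" and lists Supplement 5 in its document history. Neither of these was supplied. Its Section 6 shows disposition, medication, procedure, exposure and AE tables with separate columns for placebo double-blind and crossover data, and its Section 6.5 separates safety events in the same way. Its Section 5, however, says only: "Refer to main SAP v4.2 dated 20 SEP 2018".

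**Event rate.** SAP v4.2, Section 6.5.2, divides the number of events after first dose by total treatment duration. Supplement 7 does the same for treatment-emergent events during double-blind treatment. In both documents the only formula for duration (Section 6.5.1) ends at the last dose, while treatment-emergent events run to 30 days after it.

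**The concern.** A rule that assigns by patient is harmless while nobody has changed treatment. After crossover it moves the patient's placebo history, both events and time, into the darolutamide column and removes him from the placebo denominator.

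The patients who move are selected. Only those still on study treatment can cross over, so none can have had a double-blind withdrawal for an AE. For that table the rule enlarges the darolutamide denominator and shrinks the placebo one without moving a single event. Darolutamide then looks better tolerated than placebo even if the true risks are equal.

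The event rate is meant to adjust for unequal treatment lengths. If its numerator runs past the point where its denominator stops, rates are overstated, and more so in the arm with shorter exposure.

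**Working it through.** **1. Which analyses are exposed**

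| Analysis | Grouping stated | Exposed? |
|---|---|---|
| Safety at MFS analysis (v4.2) | Section 5 rule | No; open-label crossover has not begun |
| Safety update at final OS (v4.2, 6.5) | Section 5 rule, two groups | Yes, unless Supplement 4 or 5 overrides |
| Supplement 7: AE, exposure, disposition, medication, procedures | Split by period | No |
| Supplement 7: laboratory (6.5.4), vital signs (6.5.6), physical examination (6.5.7) | By treatment group, v4.2 safety set by reference | Unclear |

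For vital signs and physical examination, the unclear item is mainly placebo-period data. Protocol Table 4 schedules neither after the start-of-open-label visit, although Protocol 6.6.2.2 and 6.6.2.3 describe them as done at all visits (the latter except day 15).

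**2. Planning figures**

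SAP 3.1 gives 385 MFS events, diluted hazard ratio 0.71, 2:1 allocation, two-sided 0.05 and about 91% power. Freedman's formula gives Φ(√(385×2)×(1−0.71)/(1+2×0.71) − 1.96) = 0.914, so the planning set is coherent. The concern does not depend on it.

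**3. Rough number still on placebo at the MFS cut-off**

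SAP 3.1 also says: "With 40 months accrual time and a dropout rate of 40%, the study will require approximately 1500 patients", of whom 500 are on placebo. Assume that the 40% is cumulative and equal in both arms, which removes 200 placebo patients.

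- Placebo share of events, 1/(1+2×HR): 0.413 at HR 0.71 and 0.435 at HR 0.65, that is 159 or 167 of 385.
- Remaining: 500 − 159 − 200 = 141, or 500 − 167 − 200 = 133.

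Not all need cross over, so n = 50 to 140 is used.

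**4. Double-blind AE withdrawal, equal true risk**

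Assume 9% in each arm: 90 of 1000 and 45 of 500. Crossovers bring no such events.

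| n | Darolutamide | Placebo | Ratio |
|---|---|---|---|
| 50 | 90/1050 = 8.6% | 45/450 = 10.0% | 0.86 |
| 100 | 90/1100 = 8.2% | 45/400 = 11.3% | 0.73 |
| 140 | 90/1140 = 7.9% | 45/360 = 12.5% | 0.63 |

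The ratio is [1000/(1000+n)] × [(500−n)/500], whatever the common risk, so the 9% does not drive it. If 10% of crossovers later withdraw for an open-label AE, the darolutamide counts become 95, 100 and 104, and the ratios 0.90, 0.81 and 0.73.

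**5. Another AE, 20% true risk in both arms, n = 140**

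- If 10% of crossovers had it on placebo, 14 events move: 214/1140 = 18.8% v 86/360 = 23.9%.
- If 30% had it, 42 events move: 242/1140 = 21.2% v 58/360 = 16.1%.

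The direction is therefore not fixed.

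**6. Event rate with a 30-day tail**

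With constant hazard and mean exposure m months (assumed), the rate is multiplied by 1 + (30/30.44)/m: 1.041 at 24 months, 1.066 at 15 and 1.090 at 11. At 15 v 11 months a true rate ratio of 1 reads 1.0657/1.0896 = 0.978. If only 50% v 80% of patients have stopped treatment and so have a tail, it reads 1.0329/1.0717 = 0.964.

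**The case against.** The strongest reply is that the exposed analysis may be governed by a document that was not supplied. Supplements 4 and 5 postdate v4.2 by more than a year, and either could set a by-period rule. SAP 4.6.2 also allows analysis-set details in a separate document. This stands, and it is why the point is conditional. It does not remove the contradiction in the supplied text, because Supplement 7 still sends the reader back to v4.2 for its analysis sets.

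A second reply is that the opening of Supplement 7, Section 6.5, groups safety events by randomised arm and period and may be read as covering laboratory toxicities. That is possible. However, the list of split tables in its Section 6 omits laboratory, vital-sign and examination tables, so clarification is still needed.

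On the event rate, a reader might infer that the v4.2 numerator is open-ended. The documents do not support that. Appendix 9.1 of the SAP, with its footnote 10, and Protocol 6.6.1.2 record all AEs only to the end-of-study treatment visit, 28 (+7) days after last dose. Only events related to treatment or study procedures are collected beyond it. There are also two readings with no mismatch: treatment duration could mean the safety treatment period to 30 days after last dose, and Supplement 7's restriction to double-blind treatment could exclude the tail. Neither reading is stated.

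Finally, the crossover numbers and AE risks are assumptions. Crossover opens only once results are available, so further attrition before it is likely. AE withdrawal is the extreme case, v4.2 plans frequencies and not ratios, and no formal safety tests are planned.

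**Conclusion.** The point on arm assignment holds in conditional form. As written, v4.2 would place crossover patients' placebo-period events and exposure under darolutamide in the final-OS safety update, unless Supplement 4 or 5 says otherwise. Supplement 7 keeps the rule by reference and leaves the arm unclear for laboratory, vital-sign and examination data.

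The size is illustrative: a ratio of AE-withdrawal frequencies of 0.86 to 0.63 in place of 1.00. It rests on 50 to 140 crossovers, the planned arm sizes and equal true risk.

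Three stronger inferences should be resisted:

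- The safety tables at the MFS analysis are not affected.
- Supplement 7's AE and exposure tables are already separated by period.
- The distortion does not always favour darolutamide. Only the AE-withdrawal case has a direction fixed by construction.

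The event-rate point is minor. If person-time ends at last dose, rates rise by about 4% at 24 months' and 9% at 11 months' mean exposure (assumed, 30-day tail), and the rate ratio shifts by about 2% to 4% in the 15 v 11 month example. This is a small effect in a descriptive table.

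**What to change.** **Arm assignment.** In SAP Section 5, and by reference in Supplement 7, define the safety arm by the treatment actually received in the double-blind period. This still handles a darolutamide dose given in error to a placebo patient during that period. Keep placebo double-blind data under placebo in every safety table, and show post-crossover data separately wherever they are collected (mainly AEs, exposure and laboratory tests). If Supplement 4 or 5 already does this, cite it in Section 5 of Supplement 7.

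**Event rate.** Keep the summary, which Protocol 7.8.1 requires, but use one window for events and person-time. It should run from first dose to the earliest of last double-blind dose plus 30 days, first open-label dose, death or cut-off, with a separate matching window for the open-label period. Stopping at the first open-label dose keeps open-label events out of the placebo rate. The alternative is to restrict the numerator to on-treatment events.

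**Cost.** Wording in the SAP and supplement, plus table programming. No new data are needed.
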